5.9 Surgeries

Efficacy in surgical prophylaxis will be analyzed descriptively, presenting summary tables and listing on all aspects of surgical treatment and procedures as well as efficacy ratings.

The following surgery-related parameters will be presented:

- Number of minor and major surgeries

STATISTICAL ANALYSIS PLAN

Protocol No: WIL-27

Version Number: 5.0

Date of Issue: 2018-05-08

Page 22 of 27

- Location, severity (minor or major, for definitions see protocol), and type (planned or emergency) of surgery
- Expected and actual duration of surgical procedure
- Expected and actual blood loss
- Pre-, intra-, and/or postoperative IMP administration data (only listed)
- Pre-, intra-, and postoperative FVIII plasma levels (only listed)
- VWF:Ag and VWF:Ac (descriptive statistics including changes to pre-infusion)
- Presence of wound hematomas and whether or not they require surgical evacuation (only listed)
- Assessment of efficacy of surgical prophylaxis:
 1. at the end of surgery by the surgeon
 2. at end of the postoperative period by the hematologist
 3. Overall efficacy taking both the intra- and postoperative assessments into account assessed by the Investigator.
- Number of successively treated surgeries ('excellent' or 'good' overall efficacy rating)
- Concomitantly administered products (only listed)
- Narrative describing the outcome and efficacy of the intervention (only listed)
- Inhibitor testing (within 3–8 weeks after the end of the surgery, this visit may coincide with another study visit with scheduled inhibitor testing)

5.10 Safety

All safety analyses will be based on the SAF population.

The analysis of safety will include the occurrence of AEs, the results of the safety laboratory tests, immunogenicity measurements and the occurrence of parvovirus B19 seroconversions.

5.10.1 Adverse events

Adverse events (AEs) will be coded by the CRO according to Medical Dictionary for Regulatory Activities (MedDRA) version 20.0. Coding will be agreed upon with the Sponsor before database lock (cf. DMP).

All adverse events recorded since signing of the informed consent form (ICF) will be listed in appendix 16.2 of the report differentiating by treatment emergent and non-treatment emergent events. This includes also post-study serious adverse events (SAEs) which occurred up to 4 weeks after the last IMP administration (not monitored proactively), thromboembolic events monitored proactively by performing a Follow-up Contact 30 days after the completion visit as well as safety relevant information on drug overdosing, drug interactions and medication errors.

STATISTICAL ANALYSIS PLAN Protocol No: WIL-27
	
Version Number: 5.0	Page 23 of 27
Date of Issue: 2018-05-08	

The analysis will include only treatment-emergent adverse events (TEAEs), i.e. all documented AEs that started or worsened after the start of IMP infusion. It is assumed that for each increase in intensity of an AE a new entry of the AE will be done by the investigator; hence such cases will be analyzed like different phases of the same AE.

A descriptive analysis will be performed. Incidences will be presented by primary system organ classes (SOC) and incidences of PT within primary SOC sorted according to the Internationally Agreed Order.

Multiple counts within a PT or SOC (repeated or different included terms or changes in descriptors) will be counted only once for the calculation of incidences.

Global incidences will be calculated for:

- All TEAE irrespective of the causality assessment
- Related TEAEs ('Probably' or 'Possible')
- TEAEs by worst severity
- Serious TEAEs

A listing of "special cases" containing subject identification, age, sex, AE descriptors, start and end of treatment will be prepared for the following types of TEAEs:

- Serious adverse events (SAE)
- Adverse events which led to death
- Adverse events which led to discontinuation

Serious non-treatment emergent AEs will be listed separately.

5.10.2 Vital signs

Vital signs parameters (systolic/diastolic blood pressure, pulse, body weight, respiratory rates, body temperature) will be assessed at screening, PK/Non-PK visit, after 3 months at study completion visits (PK and Non-PK) and during surgery.

Descriptive analyses of values will be performed and changes from baseline will be analyzed for vital signs parameters at visits.

5.10.3 Safety laboratory variables

The analysis of the safety parameters (lab values for Hematology and Clinical chemistry) recorded during visits (screening, PK or Non-PK visit, 3-month and study completion visits (PK and Non-PK)) and at surgery will be purely descriptive and presented as summary tables or listings.

STATISTICAL ANALYSIS PLAN Protocol No: WIL-27
	
Version Number: 5.0	Page 24 of 27
Date of Issue: 2018-05-08	

Time profiles of the safety laboratory parameters will be analyzed by presenting sampling statistics for the values as well as their difference to baseline at each time point. Additionally, frequency tables for values outside the normal ranges will be presented.

Similarly, time profiles of FVIII inhibitor testing results will be analyzed by presenting sampling statistics for the values as well as frequency tables for positive findings, along with 95% Pearson-Clopper CIs. For the analysis of the inhibitor rate, in order to achieve a total number of at least 80 PTPs, data from this study will be pooled with those from previously completed clinical studies with *Wilate*.

The thromboembolic risk will be monitored by determination of VWF:Ag and VWF:Ac during the study and especially postoperatively. Descriptive statistics including changes to pre-infusion will be presented by visit and timepoint (with 95% CI) for visits or by operative day and timepoint for surgeries, respectively.

To assess the viral safety of *Wilate* incidences of parvovirus B19 seroconversions between baseline and end of study will be estimated along with 95% Pearson-Clopper CIs.

5.10.4 Other safety variables

Other safety parameters (e.g., changes in physical examination findings) will be analyzed by summary tables or listings. All abnormal findings from the physical examination will be listed.

5.11 Other variables

Not applicable.

5.12 Interim analyses

Not applicable.

6 QUALITY CONTROL

The responsible project manager will review the SAP before it is provided to the Sponsor for review. The SAP will be signed off only when approval from the Sponsor's representative is received.

Log files of all SAS® programs needed for analysis will be checked for errors, warnings and suspicious notes by the statistical programmer. All findings will be either eliminated or commented upon. The final version of each program will be stored along with its log file in the electronic archive.

All programs will be validated by the author.

STATISTICAL ANALYSIS PLAN Protocol No: WIL-27	
Version Number: 5.0	Page 25 of 27
Date of Issue: 2018-05-08	

The agreement of the program outputs with the SAP, their consistency and plausibility will be checked by the TS. Moreover, the TS will review the outputs regarding completeness, readability and comprehensibility.

8 APPENDICES

8.1 Formulas for derived variables

Variable	Description
Durations between two dates	Later date minus earlier date plus 1, expressed in days. (Remark: Duration will be 1, if both dates are the same.)
Annual bleeding rate	Number of bleedings under prophylaxis / time under prophylaxis (days)/365.25 (see prophylactic treatment phase)
AUC	Area under the curve from baseline to infinity $AUC = \sum \left(\frac{(C_n + C_{n+1})}{2} \cdot \Delta t \right) + \frac{C_{last}}{K}$ (C_{last} is the last available measurement)
AUC _{norm}	AUC normalized for the administered dose
AUMC	Area under the moment curve (from baseline to infinity) $AUMC = \sum \left(\frac{(t_n \cdot C_n + t_{n+1} \cdot C_{n+1})}{2} \cdot \Delta t \right) + \frac{C_{last}}{K^2} + \frac{t_{last} \cdot C_{last}}{K}$
CL	Clearance $CL = \frac{D}{AUC}$ where D is the actual dose administered (see remark above)
C_0	FVIII concentration before IMP administration
C_{max}	Maximal measured concentration after end of IMP infusion (peak concentration)
ED	Exposure day = each day the subject received IMP
Incremental recovery (IVR)	$IVR = \frac{(C_{max} - C_0) \cdot BW}{D}$

STATISTICAL ANALYSIS PLAN

Protocol No: WIL-27

Version Number: 5.0

Date of Issue: 2018-05-08

Page 26 of 27

	where BW stands for the body weight in kg and D is the dose according to the actual potency of the FVIII concentrate as described in above
MRT	Mean residence time $MRT = \frac{AUMC}{AUC}$
Prophylactic treatment phase	PK subgroup: (date of completion visit or date of last treatment with IMP in case completion visit not performed) – (date of first prophylactic treatment after the PK visit) Non-PK subgroup: (date of completion visit or date of last treatment with IMP in case completion visit not performed) – (date of first IMP infusion at Non-PK visit)
Success (for bleeding episodes and surgeries)	Excellent or good efficacy rating
T _{1/2}	In vivo half-life using linear regression on the terminal phase of the logarithm of the concentration; $T_{1/2} = \frac{\ln(2)}{K}$ (where K, the elimination rate constant, is determined as the slope of the regression line)
T _{max}	Time to reach maximum plasma concentration (Timing starts at end of infusion)
Vd	Volume of distribution $Vd = CL \cdot MRT$

STATISTICAL ANALYSIS PLAN Protocol No: WIL-27	
Version Number: 5.0 Date of Issue: 2018-05-08	Page 27 of 27

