5 STATISTICAL ANALYSES

All statistical analyses will be performed using SAS® for Windows (Version 9.3 or later).

Descriptive statistics will always be given for the entire population.

The analysis of safety will be based on the SAF set.

The evaluation of the primary endpoint will be performed on the FAS (ITT analysis) and on the PP set (PP analysis).

STATISTICAL ANALYSIS PLAN Protocol No: WIL-27
	
Version Number: 5.0	Page 16 of 27
Date of Issue: 2018-05-08	

For secondary endpoints, ITT and PP analyses will be carried out, unless these analysis sets differ by no more than 5% of subjects in the FAS.

Analysis of the PK properties of *Wilate* will be based on the PK set.

Analysis of the efficacy and safety of *Wilate* in surgeries will be based on the SURG set.

If not stated otherwise the following standard descriptive statistics will be presented:

Descriptive statistics for continuous data

Number of subjects (N), arithmetic mean, standard deviation (SD), minimum, lower quartile, median, upper quartile and maximum will be presented. Usually mean and quartiles will have 1 decimal more, SD 2 decimals more than the original values (as given with min, max); N has no decimals. These descriptive statistics will be determined for measured values and for differences to baseline.

Descriptive statistics for categorical data

Absolute frequencies (N) will be presented with 0, relative frequencies (%) with 1 or 2 decimals, as applicable. For changes from baseline, shift tables may be generated.

Inferential statistics

If not stated otherwise all statistical tests will be performed as described in the corresponding sections below.

All p-values will be rounded to 4 decimals (p<0.0001 will be displayed, if the p-values are less than 0.0001). Statistical significance will be declared if the rounded p-value will be less than 0.050.

All confidence intervals (CI) will be derived two-sided and at a confidence probability of $1 - \alpha = 0.95$.

Listings

All subject data will be listed by subject. Identification variable will be the subject ID (composed of study, center and subject number separated by a hyphen, e.g. '27-01-01'). Any derived data listed will also be stored permanently and will be calculated as outlined in section 8.1 of this SAP.

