5.7.1 Primary endpoint

The primary endpoint of this study is a 50% reduction of the total annualized bleeding rate (TABR) observed in the GENA-01 study with a total of 58.1 BEs per subject per year.

The efficacy of prophylactic treatment with *Wilate* will be statistically evaluated by comparing the primary endpoint, i.e., TABR under prophylaxis, with a predefined threshold of 29 per subject per year. This threshold corresponds to 50% of the TABR reported in GENA-01, a study in which previously treated adolescent and adult subjects with severe hemophilia A received on-demand FVIII treatment only.

TABR will be calculated as the total number of BEs in the time period between first dose of IMP and the Study Completion Visit, divided by the duration (in years) between first dose of IMP and the Study Completion Visit. Surgery periods, and BEs occurring within these periods, will be excluded from the calculation of TABR.

A confirmative one-sided, one-sample Poisson-test will be used to test whether the mean TABR in subjects treated prophylactically with *Wilate* is below the threshold of 29 BEs per subject year ($\alpha = 2.5\%$). A corresponding two-sided 95% CI for the TABR will also be provided.

If μ denotes the mean TABR, then the following pair of hypotheses will be tested:

$$H_0: \mu \geq 29 \text{ vs. } H_1: \mu < 29$$

The null hypothesis will be rejected (at a one-sided alpha level of 2.5%) if the upper limit of the one-sided 97.5% confidence interval for μ is strictly less than 29.

This mentioned confidence interval will be derived from a generalized linear model with a Poisson error, log-link function and log (exposure time) as offset term.

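### SAP 8.1 misprints two derivation formulas: the annual bleeding rate lacks brackets and the elimination constant K lacks a minus sign (minor correction)

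*SAP*

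**What the plan says.** **Bleeding rate.** The table in SAP 8.1 gives the annual bleeding rate as "Number of bleedings under prophylaxis / time under prophylaxis (days)/365.25", and sets durations as "Later date minus earlier date plus 1, expressed in days". SAP 5.7.1 defines TABR in words as the number of BEs "divided by the duration (in years) between first dose of IMP and the Study Completion Visit", with surgery periods and the bleeds in them left out. Protocol 3.1.1 has the same definition.

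**Elimination constant.** SAP 8.1 describes T1/2 as "In vivo half-life using linear regression on the terminal phase of the logarithm of the concentration", with T1/2 = ln(2)/K, "where K, the elimination rate constant, is determined as the slope of the regression line". The same K appears in the AUC ("Area under the curve from baseline to infinity"), whose last term is C_last/K. It also appears in the AUMC, whose last two terms are C_last/K² and t_last × C_last/K. CL, MRT and Vd are built from AUC and AUMC.

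**Status of the table.** The paragraph on listings in SAP 5 says that listed derived data "will be calculated as outlined in section 8.1 of this SAP".

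**The concern.** The bleeding-rate expression has two division signs and no brackets. By ordinary precedence it divides by days and then again by 365.25, so the days are never converted to years. The result conflicts with the SAP's own definition in 5.7.1.

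In the terminal phase concentration falls, so the slope of its logarithm on time is negative. If K is that slope, T1/2 is negative, and the AUC tail and one AUMC term are subtracted instead of added.

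The first line supplies each subject's ABR, used in the descriptive statistics and in the signed-rank comparison with the pre-study rate (SAP 5.7.2). The second supplies the half-life analysed against AB0 type and VWF:Ag, and the AUC, CL, MRT and Vd listed in SAP 5.8.

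**Working it through.** **The plan's own figure.** The documents give no numerical result from the 8.1 formulas. The only design figure on the ABR scale is power above 90% with 50 patients, mean 20, SD 15 and threshold 29 (Protocol 9.1, SAP 2.5). It reproduces: (29 − 20)/(15/√50) = 4.243; 4.243 − 1.960 = 2.283; Φ(2.283) = 98.9% (98.6% with the noncentral t). It does not use the 8.1 formulas, but it confirms that the intended scale is bleeds per patient per year.

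**1. Bleeding rate**

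- As printed, left to right: count / (days × 365.25)
- As defined in SAP 5.7.1: count / (days / 365.25) = count × 365.25 / days
- Ratio of the second to the first: 365.25² = 133,407.6, for any count and any duration

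With 10 BEs (illustrative) in 183 days (about 6 months): as printed, 10/183/365.25 = 0.0001496; as defined, 10/(183/365.25) = 19.96 per year. In 197 days (6 months + 2 weeks): 0.0001390 against 18.54. A true rate of 29 would print as 29/133,407.6 = 0.000217.

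**2. Elimination constant**

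Assumptions, none of them a result from the documents:

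- Mono-exponential decline from 100 IU/dL. This matches 50 IU/kg at 2.0% per IU/kg, the upper end of the range in Protocol 5.4.3.
- Half-life of 8, 12 or 16 h.
- Sampling times of Protocol 6.1.2 (0.25, 1, 3, 6, 9, 24, 30 and 48 h), with trapezoids from 0.25 h.
- Slope of ln(C) fitted to the 9, 24, 30 and 48 h samples.

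For 12 h: slope = −ln(2)/12 = −0.0578 per h and C(48 h) = 100 × 2⁻⁴ = 6.25 IU/dL. With K = slope, T1/2 = ln(2)/(−0.0578) = −12 h and the tail is 6.25/(−0.0578) = −108.2. With K = −slope they are +12 h and +108.2. The trapezoid part is 1655.1 either way, so AUC is 1546.9 as printed against 1763.3, a shortfall of 2 × 108.2 = 216.4, or 12%.

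| Assumed half-life | T1/2 as printed | Tail, printed / corrected (IU·h/dL) | AUC, printed / corrected | AUC shortfall | MRT, printed / corrected (h) |
|---|---|---|---|---|---|
| 8 h | −8 h | −18.0 / +18.0 | 1163.1 / 1199.1 | 3% | 9.75 / 10.90 |
| 12 h | −12 h | −108.2 / +108.2 | 1546.9 / 1763.3 | 12% | 12.22 / 16.61 |
| 16 h | −16 h | −288.5 / +288.5 | 1751.4 / 2328.5 | 25% | 14.05 / 22.46 |

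The AUC shortfall in percent does not depend on the assumed peak, because trapezoids and tail scale together. CL = D/AUC would be too high by 1199.1/1163.1 − 1 = 3%, 1763.3/1546.9 − 1 = 14% and 2328.5/1751.4 − 1 = 33%. Vd = CL × MRT follows.

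In the AUMC only t_last × C_last/K changes sign; C_last/K² does not. C_max, T_max and IVR do not use K.

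**The case against.** The best defence is that both lines are shorthand whose meaning the SAP settles elsewhere. Section 5.7.1 says years, and the closed-up spacing of the days and 365.25 suggests a unit conversion. K is named as the elimination rate constant, which is positive, and an AUC to infinity needs a tail that is added. SAP 6 has the trial statistician check outputs for plausibility, and an ABR of 0.00015 or a half-life of −12 h would stand out. The sentence in SAP 5 that points to 8.1 concerns listed data and does not say that 8.1 overrides 5.7.1. All of this stands and limits the point to a minor one. It does not make the printed formulas correct, and 8.1 is where a programmer looks for them.

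Three stronger readings are tempting and are not supported:

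- **That any bleeding rate would pass the threshold of 29.** Under SAP 5.7.1 and Protocol 9.2.2 the decision rests on a confidence limit from a Poisson model of counts with log exposure time as offset. The 8.1 ratio does not enter it. What is missing there is the unit of exposure time: with days, the model gives a daily rate, and 29 per year corresponds to 29/365.25 = 0.079 per day.
- **That the unstated base of the logarithm permits log10.** T1/2 = ln(2)/K holds only for a natural-log slope, so the base is implied.
- **That a programmer would correct the sign for T1/2 but not for the tails.** K is defined once and used throughout; this would require two values of K with opposite signs. It is possible but conjectural.

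**Conclusion.** SAP 8.1 is wrong as printed in two places. The ABR factor is exactly 365.25², about 133,400, on the usual left-to-right reading; with brackets around days/365.25 the line is right and agrees with SAP 5.7.1 and Protocol 3.1.1. The sign error in K holds for any declining curve. Its effect on AUC, about 3% to 25% too low, rests on the assumed half-lives of 8 to 16 h and mono-exponential decline. Total AUC stays positive in all three cases, so it would look less odd than the negative half-life beside it.

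The reach is per-subject ABRs and the PK parameters that depend on K. For the signed-rank comparison, the ABR error would matter if only the on-study rate carried it; a common factor on both rates would leave the ranks unchanged. The primary test is not computed from the 8.1 ratio. This is a minor correction.

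**What to change.** In SAP 8.1:

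- Write ABR = number of BEs / (days / 365.25). Define days as the TABR observation time of 5.7.1 after excluding surgery periods. This needs saying because 8.1 refers instead to the prophylactic treatment phase, which for PK subjects starts after the PK visit, and its formula does not mention surgery.
- Write K = −(slope of the least-squares line of natural-log concentration on time in the terminal phase). The T1/2, AUC and AUMC formulas can then stay as they are.

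In SAP 5.7.1, state that the exposure time in the model offset is this same time in years, so that the estimated rate and its confidence limit are comparable with 29. SABR follows by analogy with its threshold of 19.1.

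The cost is two lines in 8.1 and a clause in 5.7.1. No design feature, data collection or clinical rule changes.

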6.1.2 PK Visit

Patients will receive *Wilate* at a dose of 50 ± 5 IU/kg (labelled dose) after a washout period of at least 72 hours from their last FVIII injection. Patients must not be experiencing any bleeding.

The following assessments will be performed:

- **Body weight** before injection
- Blood samples will be taken for the following purposes and at the following time points:
 - **FVIII:C plasma concentration (OS and CHR) for PK assessment** within 1 h before injection and 15 ± 5 min, 1 h (± 5 min), 3 h (± 15 min), 6 h (± 30 min), 9 ± 1 h, 24 ± 2 h, 30 ± 2 h, and 48 ± 2 h after the end of injection
 - **Safety laboratory** before and 48 ± 2 h after injection
 - **FVIII inhibitor** before injection
 - Plasma **VWF:Ag** and **VWF:Ac** within 1 h before injection and 15 ± 5 min after the end of injection
 - **Parvovirus B19 antibodies** before injection
 - **Retention sample** for possible additional virus marker testing before injection
- **Vital signs** before injection as well as 1 h (± 5 min) and 48 ± 2 h after injection
- **AE monitoring**
- **Concomitant medications**

At the end of this visit, patients will **receive a patient diary**. The Investigator will explain to the patient how to fill in the diary and emphasize the importance of carefully documenting all treatment details, AEs, and concomitant medications. Also, patients will be **provided with IMP** for home treatment. They will be re-supplied whenever necessary during the study.

The first prophylactic injection of *Wilate* after the PK Visit marks the beginning of the Prophylactic Treatment Phase.

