6.1.3 Non-PK Visit

The Non-PK Visit is intended only for patients *not* undergoing PK assessments.

During the Non-PK Visit, the first prophylactic injection of *Wilate* will be administered, if possible after a washout period of at least 72 hours from the patient's latest FVIII injection. Patients must not be experiencing any bleeding.

The following assessments will be performed:

- **Body weight** before injection
- Blood samples will be taken for the following purposes and at the following time points:
 - **FVIII:C plasma concentration (OS and CHR) for IVR assessment** within 1 h before injection of the first prophylactic dose and 15±5 min after the end of the injection
 - **Safety laboratory** before and 15±5 minutes after injection
 - **FVIII inhibitor** before injection
 - Plasma **VWF:Ag** and **VWF:Ac** within 1 h before injection and 15±5 min after the end of injection
 - **Parvovirus B19 antibodies** before injection
 - **Retention sample** for possible additional virus marker testing before injection
- **Vital signs** before and 15±5 min after injection
- **AE monitoring**
- **Concomitant medication**

At the end of this visit, patients will **receive a patient diary**. The Investigator will explain to the patient how to fill in the diary and emphasize the importance of carefully documenting all treatment details, AEs, and concomitant medications. Also, patients will be **provided with IMP** for home treatment. They will be re-supplied whenever necessary during the study.

The first prophylactic injection of *Wilate* administered during the Non-PK Visit marks the beginning of the Prophylactic Treatment Phase.

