6.1.5 Day-30 Visit

The Day-30 Visit will take place 30±3 days after the start of the Prophylactic Treatment Phase. The following assessments will be performed:

- **Same assessments as for Day-14 Visit**

6.1.6 3-Month Visit

The 3-Month Visit will take place 3 months (±2 weeks) after the start of the Prophylactic Treatment Phase. A prophylactic injection of *Wilate* will be administered, and the following assessments will be performed:

- **Review of patient diary**
- **Body weight** before injection
- Blood samples will be taken for the following purposes and at the following time points:
 - **FVIII:C plasma concentration (OS and CHR) for IVR assessment** within 1 h before injection of the prophylactic dose and 15±5 min after the end of the injection
 - **Safety laboratory** before injection
 - **FVIII inhibitor** before injection
 - Plasma **VWF:Ag** and **VWF:Ac** within 1 h before injection and 15±5 min after the end of injection
- **Vital signs** before and 15±5 min after the end of injection
- **AE monitoring**
- **Concomitant medication**

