Regarding efficacy in the treatment of BEs, confirmatory statistical testing will test the null hypotheses that the percentage of success is $\leq 70\%$ (alternative hypothesis: percentage $> 70\%$); the test procedure based on the generalized estimation equation will take into account several BEs in one patient as correlated repeated measurements.

Thus, if π denotes the proportion of success, then the following pair of hypotheses will be tested:

$$H_0: \pi \leq 0.7 \text{ vs. } H_1: \pi > 0.7$$

Pharmacokinetic Analysis

FVIII:C will be measured in the vials used for PK injections as well as in plasma using the CHR and OS assays.

- AUC of *Wilate* will be calculated from FVIII:C plasma levels measured at predefined time points and normalized for the administered dose (AUC_{norm}) using actual IMP potencies.
- All other PK parameters will be calculated from FVIII:C plasma levels measured at predefined time points using actual IMP potencies.
- Incremental IVR will be calculated from FVIII:C plasma levels measured before injection and peak levels obtained in the 15-min post-injection sample using actual IMP potencies.

The PK profiles of *Wilate* and the PK parameters derived from them will be summarized by descriptive statistics as well as the presentation of concentration vs. time plots.

For all patients, the results of the IVR assessments over time will also be analyzed in summary tables for each time point and their differences to baseline along with 95% CIs for the mean differences.

Analysis of variance (ANOVA) will be used in an exploratory sense to assess a possible association between AB0 blood type, VWF:Ag, and the FVIII:C half-life of *Wilate*.

Analysis of Other Secondary Endpoints

The statistical analysis of other secondary endpoints will be descriptive, including exploratory 95% CIs for the location parameters.

Subgroup Analyses

The analyses of the efficacy endpoints ‘efficacy of prophylactic treatment’ and ‘efficacy in treatment of breakthrough BEs’ will be presented for the following subgroups:

- Age (‘<17 years’ and ‘≥17 years’)
- Race (‘American Indian or Alaska Native,’ ‘Asian,’ ‘Black or African American,’ ‘Native Hawaiian or Other Pacific Islander,’ ‘White,’ ‘Other’);
- Geographical region (‘patients in the US,’ ‘patients outside the US’);

Analysis of PK parameters will be presented by age (‘< 17 years’ and ‘≥17 years’).

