3.2 Deviations from the trial protocol with regard to statistical analyses

No deviations from the protocol are planned.

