5.8 Pharmacokinetics / Pharmacodynamics

For Pharmacokinetics and IVR assessments FVIII:C will be measured by both, the chromogenic (CHR) and one-stage assay (OS) and analyzed based on actual IMP potency.

The PK profiles of *Wilate* and the PK parameters derived from them will be summarized by descriptive statistics as well as the presentation of concentration vs. time plots based on the PK set. In the analysis of the PK profiles geometric means and standard deviations will be presented in addition to the arithmetic means and standard deviations.

The following PK parameter will be derived and presented using a non-compartment model:

- Area under the curve (AUC) and AUC normalized for the administered dose (AUC_{norm})
- FVIII in vivo half-life ($T_{1/2}$)
- Maximum plasma concentration (C_{max})
- Time to reach maximum plasma concentration (T_{max})
- Mean residence time (MRT)
- Volume of distribution (Vd)
- Clearance (CL)
- Incremental in vivo recovery (IVR)

Analysis of variance (ANOVA) will be used in an exploratory sense to assess a possible association between AB0 blood type, VWF:Ag, and the FVIII:C half-life of *Wilate*.

IVR will be analyzed for the FAS and additionally for the PP population if these populations differ by >5%. The results of the IVR assessments over time will be analyzed in summary tables for each time point and their differences to baseline along with 95% CIs for the mean differences.

To compare the pharmacokinetic characteristics of the 6-months PK-profile with those of the baseline PK-profile a matched-pairs sign rank test of the null hypothesis of no time difference will be performed at for all PK parameters.

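### SAP 8.1 bases incremental recovery on Cmax rather than the protocol's 15-minute sample, which inflates PK patients' baseline and 6-month IVR relative to month 3 and to non-PK patients

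*SAP*

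**What the plan says.** Protocol 9.2.2 (Pharmacokinetic Analysis) derives incremental IVR from the pre-injection level and "peak levels obtained in the 15-min post-injection sample using actual IMP potencies". SAP 8.1 instead sets IVR to (Cmax - C0) x BW / D, where Cmax is "Maximal measured concentration after end of IMP infusion (peak concentration". Nothing else in the SAP restricts Cmax to the 15-minute sample. The same table defines Tmax as the time at which the maximum is reached, which makes sense only if Cmax is taken over the whole profile.

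The number of samples behind that maximum depends on visit and cohort. PK patients are sampled "within 1 h before injection and 15 ± 5 min, 1 h (± 5 min), 3 h (± 15 min" and onward to 48 h at the PK Visit (Protocol 6.1.2), and on the same schedule at the PK Study Completion Visit (6.1.7). At the 3-Month Visit (6.1.6) all patients are sampled only "within 1 h before injection of the prophylactic dose and 15±5 min after the end of the injection". Non-PK patients are sampled "within 1 h before injection of the first prophylactic dose and 15±5 min after the end of the injection" at the Non-PK Visit (6.1.3), and likewise at their completion visit (6.1.8).

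SAP 5.1.1 takes the first IVR, at the PK or Non-PK Visit, as baseline. SAP 5.8 analyzes IVR in the FAS, so both cohorts are pooled: "The results of the IVR assessments over time will be analyzed in summary tables for each time point and their differences to baseline", with 95% CIs for the mean differences. SAP 3.2 states: "No deviations from the protocol are planned".

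**The concern.** IVR over time is a secondary endpoint (Protocol 3.1.2, SAP 5.7.2). It is there to show whether recovery is stable under treatment. The highest of several values measured with error exceeds any one of them on average, even when the true peak is at 15 minutes. In PK patients the SAP rule therefore raises baseline and 6 months but not month 3, and so builds in a dip at month 3. It also puts PK and non-PK patients on different scales at baseline and at 6 months before they are pooled. This is bias rather than noise: more patients would only narrow the interval around the wrong value.

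**Working it through.** The plan states no figure for IVR, so there is none to reproduce. The check is a count of samples, an inequality, and a simulation of the size.

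**Post-dose samples entering Cmax**

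| Visit | PK patients | Non-PK patients |
|---|---|---|
| Baseline | 8 (0.25, 1, 3, 6, 9, 24, 30, 48 h) | 1 |
| 3 months | 1 | 1 |
| 6 months | 8 | 1 |

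**Direction.** Write C15 for the 15-minute level. The SAP value minus the protocol value is (Cmax - C15) x BW / D. This is never negative, because C15 is one of the values over which the maximum is taken. It is zero in every profile only if the 15-minute sample is always the highest. The relative inflation of IVR is (Cmax - C15) / (C15 - C0).

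**Size.** The documents give no assay error, half-life or peak timing. Assumptions: single-exponential decline from 15 minutes; half-life 8 to 15 h; independent lognormal error with a CV of 5% to 15%; C0 = 0. A positive C0 would make the relative effect larger. Expected inflation is E[max of 8 samples] / E[C15] - 1, from 400,000 simulated profiles per setting. Brackets show how often a later sample is the maximum.

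| Half-life | CV 5% | CV 10% | CV 15% |
|---|---|---|---|
| 8 h | 0.7% (18%) | 2.9% (33%) | 5.9% (42%) |
| 10 h | 0.9% (23%) | 3.5% (38%) | 6.8% (46%) |
| 12 h | 1.1% (27%) | 4.0% (42%) | 7.5% (49%) |
| 15 h | 1.4% (32%) | 4.6% (46%) | 8.5% (53%) |

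With no measurement error the inflation is 0%.

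If true levels are flat over the first hour, two samples share the same mean, and for normal errors the expected maximum exceeds that mean by about CV / sqrt(pi). That is 5% / 1.772 = 2.8% and 10% / 1.772 = 5.6%; the later samples raise the upper end to about 6%. If the 1-hour level is truly 5% above the 15-minute level, inflation is 5.0% to 8.8% (half-life 12 h, CV 0% to 10%).

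**Effect on the planned contrast.** With inflation b in PK patients, their month-3 difference from baseline is biased by -b. With 20 PK patients among 50 evaluable, the pooled bias is -(20/50) x b = -0.4b:

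- Peak at 15 minutes, CV 5% to 10%: -0.4 x 0.7% = -0.3% to -0.4 x 4.6% = -1.8%.
- Flat first hour: -0.4 x 3% = -1.2% to -0.4 x 6% = -2.4%.

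Protocol 5.4.3 puts recovery at 1.5 to 2.0% per IU/kg. On that scale the first case is 1.5 x 0.007 = 0.01 to 2.0 x 0.046 = 0.09 in PK patients. Multiplied by 0.4, it is 0.004 to 0.04 pooled.

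The 6-month minus baseline difference uses the same 8-sample rule at both visits in PK patients and one sample at both in the others, so there the bias largely cancels.

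**The case against.** Several points on the other side are fair.

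- **Protocol version.** SAP section 1 cites a protocol of 2017-09-07 with Amendment #04; the protocol available here is dated 16-Jan-2017. The two sets of documents differ elsewhere too, for instance in the subgroup age cut (17 against 16 years). If the later version changed the IVR rule, the charge of an undeclared deviation falls away. The unequal sampling does not.
- **Mechanism.** Eight samples overstates it. Under single-exponential decline the 1-hour sample alone accounts for 87% to 100% of the inflation, so in effect this is a maximum of two or three values. The simulated figures already reflect that. Error shared by all samples of a profile would shrink them.
- **Precision.** With n = 50 and one measurement at each of two visits, assay error alone gives a 95% CI half-width of 1.96 x sqrt(2) x CV / sqrt(50), which is 2.0% at CV 5% and 3.9% at CV 10%. The pooled bias at the same CV lies inside that. It is still systematic, and in PK patients it is 2.5 times as large (1 / 0.4).
- **Use of the result.** No hypothesis or threshold attaches to the month-3 change, and the primary endpoint is untouched. If all 55 enrolled patients enter the FAS, the affected share is 20/55 = 36% rather than 40%.
- **Other differences between visits.** PK visits use 50 ± 5 IU/kg and the other IVR visits a prophylactic dose. The 72-hour washout is required at the PK Visit, applies only if possible at the Non-PK Visit, and none is stated for month 3. Changing the sample does not remove these.

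These points limit the size and consequence of the problem. None of them makes the Cmax rule appropriate for IVR.

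**Conclusion.** The concern holds. The SAP definition conflicts with the supplied protocol and, because sampling is unequal, applies a different measurement rule by visit and cohort within one table. What is affected is the month-3 difference from baseline in PK patients and in the pooled FAS, the IVR levels at baseline and 6 months, and any comparison of PK with non-PK patients at those visits. An apparent rise from month 3 to month 6 would show in the summary table, but the planned 6-month difference from baseline is largely protected.

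The direction is certain. The size is modest and depends on the half-life, measurement error and peak timing assumed above; it would be near zero if the 15-minute sample were nearly always the highest. This should be corrected before analysis, but it does not threaten the trial's main conclusion.

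**What to change.** In SAP 8.1, define IVR as (C at 15 min - C0) x BW / D for every patient and every IVR visit, as Protocol 9.2.2 does, and keep Cmax as a separate parameter of the full PK profiles. If a Cmax-based recovery is also wanted, report it as supplementary for the PK set only. Check the 2017-09-07 protocol; if it changed the IVR rule, say so in the SAP and still use one sample rule at all visits. Showing IVR by cohort as well as pooled would expose the remaining dose and washout differences.

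The cost is one definition and one line of derivation code, since the 15-minute sample is already scheduled at every IVR visit. The one small loss is that a PK patient with no 15-minute sample would have no IVR at that visit, where the Cmax rule would have filled the gap from a later sample.
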